Recognizing the ED as a unique opportunity to address COVID-19 booster vaccine hesitancy in underserved populations, we will launch the PROmotion of COVID-19 BOOSTer VA(X)ccination in the Emergency Department (PROBOOSTVAXED) trial as an extension of the PROCOVAXED trial, seeking to increase COVID-19 booster vaccine acceptance and uptake among vaccinated ED patients. Because of Omicron variant-associated surges during the COVID-19 pandemic with corresponding research staff illness and ED overcrowding, we found

wide week-to-week fluctuations in enrollment in the PROCOVAXED study. To reduce this variability of enrollment, we have changed the unit of randomization from 1-week to 1-day in the PROBOOSTVAXED trial.

IMPORTANT CHANGE: Under intense political pressure and in response to Congress' reluctance to spend more on COVID-19 pandemic relief, the Biden administration recently made two announcements: 1) the national public health emergency declaration regarding the COVID-19 pandemic will be left to expire as of January 11, 2023, and 2) the administration will end their provision of free COVID-19 vaccines, testing and therapeutics, shifting the costs for vaccines, testing and treatments to health insurers and patients via commercial payment mechanisms. Because of these changes in reimbursement, we have been informed that only some of the PROBOOSTVAXED study sites will have COVID-19 vaccines available for distribution in the ED, whereas others will not. Nevertheless, we will proceed with the same research protocol, however, we will be performing additional subgroup analyses that compare 30-day vaccine uptake in sites with available COVID-19 vaccine to those without for the intervention and control arms.

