The primary outcome for Specific Aims I and III is **30-Day COVID-19 Booster Vaccine Uptake**, which will be ascertained by review of ED electronic health records (EHRs) at 30 days and follow-up phone calls. For Specific Aim I, this primary outcome will be compared between the Intervention M arm (Messaging + Vaccine Acceptance Question) and the Control arm (No Messaging, No Vaccine Acceptance Question). For Specific Aim III, this primary outcome will be compared between the Intervention Q arm (Vaccine Acceptance Question, No Messaging) and the Control arm (No Messaging, No Vaccine Acceptance Question).

Primary Outcome for Specific Aim II: Booster Vaccine Acceptance in the ED

The primary outcome of Specific Aim II is **COVID-19 Booster Vaccine Acceptance** in the ED, which will be ascertained by a survey question of study participants in the ED. This outcome will be compared between the Intervention M arm (Messaging + Vaccine Acceptance Question) and the Intervention Q arm (Vaccine Acceptance Question, No Messaging).

II. IRB

We will submit our protocol to the UCSF Committee on Human Research as a modification. We will continue with multi-site reliance mechanism for the PROCOVAXED study as per NIH guidelines for randomized trials.

III. Deposition of Protocol into ClinicalTrials.Gov

As per federal regulations, we will deposit our full study protocol into the repository https://clinicaltrials.gov/.

IV. Setting and Sites

We will conduct this over six months (mid-September 2023 to February 28, 2024) at five high-volume EDs in four cities: (Zuckerberg San Francisco General, UCSF Parnassus Medical Center [San Francisco, CA], Thomas Jefferson University Hospital [Philadelphia, PA], Ben Taub Hospital [Houston, TX], Duke University Medical Center [Durham, NC]). We have chosen this time-period to coincide with typical waves of the COVID-19 pandemic.

V. Randomization

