The outcome is booster vaccine acceptance (defined as a response of "yes" to the question "Would you accept the booster vaccine in the emergency department today if your doctor asked you?"). This outcome will be compared using mixed logistic regression with a fixed effect for randomization assignment, a normally distributed random effect to allow for clustering by enrolling center, and restricted cubic splines to allow for secular trends during the study period. The treatment effects will be tested by the coefficient for the fixed effect of study arm along with 95% confidence intervals.

Analysis for Specific Aim III

For Specific Aim III, the outcome is uptake (receipt) of a booster vaccine at any vaccination location within 30 days of the index ED visit. We will compare outcomes in participants seen on Intervention Q arm dates with those seen on Control dates to test our study hypothesis: Implementation of an ED protocol in which patients are asked whether they will accept a booster vaccine (and notifying ED providers when they say they will accept it) will be associated with increased booster vaccine uptake in vaccinated ED patients.

A secondary outcome for Specific Aim III is receipt of a booster vaccine during the index ED visit, comparing participants seen on Intervention Q dates with those seen on Control dates - ascertained by check of the participant's EHR on the day after their ED visit.

Subgroup Analyses

Another focus of this research is on ED patients who lack primary care group, defined on the Intake survey question: "Do you have a regular clinic or doctor for medical care?" We will analyze outcomes according to the binary indicator of having primary care – yes versus no (and unsure).

We will additionally stratify outcomes by study site (representing different regions of the country and different communities), vaccine administration capability, age, gender, primary language, and race/ethnicity.

Subgroups will be tested by adding a subgroup by intervention interaction to the mixed logistic regression. A subgroup will be considered significant if the pairwise intervention by subgroup omnibus test is significant at the 0.05 level.

Rationale for time (1-day unit) cluster and consideration of Alternative Study Designs:

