Statistical approach: In terms of statistical approach, this is a superiority trial in which we seek to verify our central study hypothesis that provision of booster vaccine messaging will result in greater acceptance and uptake of the booster vaccine. Following the recommendations of Hussey and Hughes, our statistical analyses will focus on comparing the vaccine uptake rates during the time periods when booster vaccine messaging is in place (Intervention M) and when the system is not in place (Control - usual care) using mixed effects logistic models. The outcome of interest is the binary indicators of whether they have received a booster vaccine in the ED (uptake - yes/no). Models will include a normally distributed random center effect (on the logit scale) to accommodate potential within-center characteristics (e.g., case mix, demographics), as well as terms for time and intervention. Hypotheses testing will focus on the statistical significance of the intervention indicator. We will fit the mixed effects models using maximum likelihood and routines in Stata.

We will test our primary hypotheses and analyze outcomes according to the study arm (index visit in Intervention M day versus control day) to which patients were allocated, regardless of whether they received booster vaccine messaging or not - *intention to treat analysis*.

In addition to the effects on *total* vaccine acceptance, we will also examine the effect of booster vaccine messaging on acceptance in patient sub-groups, especially African American and Latinx persons. Booster vaccine messaging may work for one patient sub-group and not others -- these additional analyses will guide future directions and modifications of booster vaccine messaging.

XVI. Data Management Plan

We will manage data using REDCap, hosted by the core site (UCSF) for secure data entry and management. Patient identifiers (medical record numbers and phone numbers) only link will be

to unique study ID numbers, which will be housed in files that are kept separate from other study data. We will develop a detailed data dictionary to ensure consistent standards across sites. We will reduce missing or erroneous data using the REDcap data quality tool.

XVII. Sample Size Considerations

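### Seven subgroup factors are each judged at an unadjusted 0.05, about a 30% chance of a false subgroup claim per outcome and arm pair, and the vaccine-availability contrast rests on five sites

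*Combined protocol and SAP*

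**What the plan says.** Section XV, Subgroup Analyses, names seven factors. Primary care comes first: "We will analyze outcomes according to the binary indicator of having primary care". Site follows: "We will additionally stratify outcomes by study site". The list then continues with "vaccine administration capability, age, gender, primary language, and race/ethnicity". The method is an interaction test: "Subgroups will be tested by adding a subgroup by intervention interaction to the mixed logistic regression". The decision rule is: "A subgroup will be considered significant if the pairwise intervention by subgroup omnibus test is significant at the 0.05 level".

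The paragraph on the important change in the Overview says that only some sites will have vaccine to give in the ED. It adds analyses that "compare 30-day vaccine uptake in sites with available COVID-19 vaccine to those without", by arm. Section IV places the trial "at five high-volume EDs in four cities".

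The models in Section XV have a fixed effect for arm, terms for time and a normally distributed random effect for centre. No centre-by-arm term is described. Under Statistical approach, after raising subgroup effects on acceptance, the plan says that "these additional analyses will guide future directions and modifications of booster vaccine messaging".

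The document contains no multiplicity adjustment. It does not call the subgroup analyses exploratory, and it does not list the outcomes and arm pairs to which the rule applies.

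**The concern.** Two separate problems sit under one rule.

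The first is multiplicity. The rule attaches the word significant to any one of seven tests that reaches 0.05. The chance that at least one does so by luck is well above 0.05, and the plan intends subgroup results to shape later messaging.

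The second is the unit of inference for vaccine availability. Sites were not randomised to have vaccine. Five sites, some with and some without, also differ in region, community and case mix. A random centre effect absorbs differences between sites in the overall level of uptake. It does not absorb differences between sites in the arm effect. Without a term for those, the availability-by-arm interaction is judged with participant-level precision although only five sites inform it. Because the Overview singles this analysis out, readers will look for it.

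**Working it through.** **Inputs from the documents.** Seven factors, 0.05 each (Section XV). Five sites (Section IV). Control uptake 5%, increase 7 points, 248 per arm, 744 in total (Section XVII).

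**Assumptions not in the documents.** Equal enrolment by site (about 50 per arm per site). Two sites with vaccine and three without, with one against four as a variant. SD of site log odds ratios from 0 to 0.5. A higher-rate outcome of about 30% against 40% to stand for acceptance. For the joint simulation, subgroup prevalences and the number of age and race categories.

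**Step 1: the plan's own figure.** The plan gives no error rate for the subgroup family, so the only figure to reproduce is the sample size. With pooled variance, two-sided 0.05 and 80% power:

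n = [1.96·√(2·0.085·0.915) + 0.8416·√(0.05·0.95 + 0.12·0.88)]² / 0.07² = 247.98, so 248 per arm and 744 in total.

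This matches, and supports reading the effect as 5% to 12%.

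**Step 2: multiplicity.** With no true interaction and independent tests, P(at least one hit) = 1 − 0.95^k.

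| Tests | Coverage | Probability |
|---|---|---|
| 7 | one outcome, one arm pair | 30.2% |
| 14 | two families | 51.2% |
| 21 | three aim comparisons | 65.9% |

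A joint simulation of all seven interaction tests in the same 496 participants (likelihood-ratio tests, site as fixed effects, availability nested in site, 1,000 runs) gave 29.9% at 30%/40%. It gave 37.4% at 5%/12%, where sparse events make individual tests somewhat liberal (5.2% to 8.1% each). The Monte Carlo standard error near 30% is √(0.3·0.7/1000) = 1.4 points. Dependence between the seven tests therefore does not bring the 30% down.

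**Step 3: availability by arm.** Let τ be the SD of the site log odds ratios for reasons other than availability, and v the sampling variance of one site's log odds ratio. The site-split factor (1/2 + 1/3) multiplies both and cancels, so in large samples the false-positive rate is 2Φ(−1.96/√(1 + τ²/v)).

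- Uptake: v = 1/(50·0.05·0.95) + 1/(50·0.12·0.88) = 0.610. The rate is 5.0% at τ = 0, 6.7% at 0.3 and 9.9% at 0.5.
- Higher-rate outcome: v = 1/(50·0.3·0.7) + 1/(50·0.4·0.6) = 0.179. The rate is 5.0%, 11.0% and 20.6%.

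Simulation with Mantel-Haenszel log odds ratios stratified by site (two against three, 20,000 runs per setting) gave:

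| τ | Uptake 5%/12% | Higher-rate outcome |
|---|---|---|
| 0 | 4.1% | 5.0% |
| 0.3 | 5.7% | 10.5% |
| 0.5 | 9.0% | 19.3% |

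The likelihood-ratio version in the joint simulation gave 5.7% and 5.5% at τ = 0, and 10.6% and 20.0% at τ = 0.5. With one site against four, uptake gave 2.7% at τ = 0 and 6.6% at τ = 0.5, after leaving out about 10% of runs in which the contrast could not be estimated.

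For scale, the planned log odds ratio is ln(0.12/0.88) − ln(0.05/0.95) = 0.952, an odds ratio of 2.59. At τ = 0.3, 95% of site odds ratios would lie in exp(0.952 ± 1.96·0.3), or 1.4 to 4.7. At τ = 0.5 the range is 1.0 to 6.9.

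**Step 4: how thin the site data are.** Control participants per site: 248/5 = 49.6, so 49.6·0.05 ≈ 2.5 expected events. P(no event at a site) = 0.95^49.6 = 0.079. P(at least one of five sites has none) = 1 − (1 − 0.079)^5 = 34%. At such a site the log odds ratio cannot be estimated, whereas a risk difference still can.

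**The case against.** The plan has real safeguards. The factors are named in advance. Each gets an interaction test rather than separate p-values within subgroups, with one omnibus test per factor. The Statistical approach text centres hypothesis testing on the intervention indicator and gives subgroup results a role in guiding future work, which is close to hypothesis generation. All of that stands, and it keeps the point modest.

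Some stronger readings go further than the documents allow:

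- A reader might infer that a false subgroup claim is more likely than not. For one outcome and one arm pair the figure is about 30%. Even odds need 14 or more independent tests. The words pairwise and outcomes suggest repetition across arms and endpoints, but pairwise could also mean only a two-way interaction.
- A reader might infer that the plan breaks a 5% error rate that it promises. It does not: 0.05 is stated as the level of each test, and no family-wise rate is claimed.
- A reader might infer that the availability interaction certainly has intervals that are too narrow. That depends on arm effects varying between sites, and the documents give no such variance. Having five sites does not by itself inflate the test.

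It is also fair that no wording removes the confounding of availability with site, and that the Overview promises a comparison, not a causal claim. Section XIV logs ED vaccine availability for the patients approached, so it may vary somewhat within a site, but the Overview defines the comparison by site. These points favour describing the contrast over testing it.

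**Conclusion.** The concern holds in limited form. The rule carries about a 30% chance of at least one false subgroup claim per outcome and arm pair when no interaction exists. That rises to about 66% if it is applied as 21 independent tests, a coverage the plan leaves open.

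For vaccine availability, the described model gives a test that is near nominal if arm effects are the same at all sites (about 3% to 6% across the site splits and test forms tried). It is too liberal if they are not: about 6% to 9% for uptake and 10% to 20% for a higher-rate outcome, at an assumed SD of 0.3 to 0.5 with two sites against three. The size of this effect rests on those assumptions. That availability cannot be separated from other differences among five sites does not.

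A reader might go on to infer that the Aim I result is in doubt. Nothing here supports that, since the subgroup rule plays no part in the primary test. This is an improvement worth making, not a serious flaw.

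**What to change.** Replace the decision-rule sentence with text to this effect:

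> All subgroup analyses are exploratory. For each factor we will report interaction estimates with 95% confidence intervals, list the outcomes and arm pairs examined, and state the total number of interaction tests. An unadjusted p-value below 0.05 will not be described as a significant subgroup difference. For study site and ED vaccine availability we will show the five site-specific risk differences between arms, marked by availability, without a significance test at participant-level precision.

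An adjusted threshold confined to the Aim I contrast (for example 0.05/7 = 0.0071, which holds the family-wise rate at 4.9% for seven independent tests) is not recommended. It would rule out any claim on acceptance by race and ethnicity, the subgroup question that the Statistical approach text stresses.

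The cost is wording in the analysis plan only. The trial gives up confirmatory subgroup claims, but Section XVII sizes it for the overall Aim I comparison and not for interactions.
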